7.1.4.14 Time to clinical treatment failure

The time to clinical treatment failure (in days) is defined as:

(Date when any one of the criteria defining the composite endpoint occurred for the first time – Date of initiation of study treatment),

where acute COPD exacerbations experienced during the study and their characteristics are recorded on the 'Acute Exacerbation COPD' form of the eCRF, i.e. in particular:

- Date of first antibiotic intake and/or first systemic corticosteroid intake for treating the COPD exacerbation
- Date of hospitalisation admission for the COPD exacerbation
- Date of emergency room admission (emergency room admission for longer than 24 hours will qualify as a hospitalisation) for the COPD exacerbation
- Date the COPD exacerbation (assessed as an AE) results in death.

Table 6: Criteria for event/censored for assessment of Time to clinical treatment failure

Situation	Date of event or Censoring	Time to clinical treatment failure	Outcome
Subjects who had any one of the criteria defining the composite endpoint	Date of clinical treatment failure after entering in study	(Time from initiation of study treatment until Date of clinical treatment failure after entering in study)	Event
Subjects who never had any one of the criteria defining the composite endpoint in study period	Withdrawal or last contact date	(Time from initiation of study treatment until Date of withdrawal or last contact date)	Censored
Subjects who died (not COPD-related)	Death date	(Time from initiation of study treatment until Date of death)	Censored
Subjects who withdrew or were lost to follow-up during the study	Withdrawal or last contact date	(Time from initiation of study treatment until Date of withdrawal or last contact date)	Censored

7.1.4.15 Chronic Respiratory Questionnaire (CRQ)

The CRQ is an instrument developed to measure quality of life of patients with COPD. The CRQ contains 20 questions which can be divided into four domains: dyspnoea (5 questions), fatigue (4 questions), emotional function (7 questions) and mastery (4 questions; the subject's feeling of control over their disease). The dyspnoea component is "individualised" (not standardised) which means that it is made up of five activities chosen by a patient to cause the greatest shortness of breath. The patient then rates the dyspnoea on these five most important activities on a 7-point scale which spans from 1 (extremely short of breath) to 7 (not at all short of breath). Every subject will have a unique list of activities. The questions covering the dimensions of fatigue, emotional function, and mastery are standardised and the subject is offered an appropriate 7-point scale for each question ranging from 1 (maximum impairment) to 7 (no impairment). The results are expressed as the mean score for each domain (i.e. the total score per domain divided by the corresponding number of items) and the mean total score (i.e. the mean of the scores from the 3 domains fatigue, emotional function and mastery). (Refer Appendix D).

The four domain scores will be calculated based on:

- Dyspnoea from questions 1, 2, 3, 4, 5
- Fatigue from questions 8, 11, 15, 17
- Emotional function from questions 6, 9, 12, 14, 16, 18, 20

- Mastery from questions 7, 10, 13, 19.

The score will be applied at Baseline, at Day 14, and Weeks 8, 12 and 26 and will allow an evaluation of the improvement of subject well-being throughout the study.

7.1.4.16 Cumulative oral/IV steroid dose

The cumulative oral/IV steroid dose during the duration of current COPD exacerbation will be derived on a patient level from the 'Prior (Last 6 months medication) and Concomitant Medication' form of the eCRF. The medications recorded on this form to be considered for this exploratory endpoint will verify:

- Systemic corticosteroids: ATC code 'H02'
- Route 'IV = intravenous' or 'PO = oral'
- Medication administered for COPD exacerbations only (i.e. with indication = 'COPD exacerbation: current/during the study') and taken during the duration of current COPD exacerbation (i.e. from the date when symptoms started until the date when symptoms stopped).

Moreover, the dose of treatment recorded on the form for selected systemic corticosteroids will be converted to 'mg', in case the unit recorded on the form is not 'mg'.

Then a correction factor will apply on the oral/IV steroid dosages (mg) using dosing equivalencies, i.e.:

- 1 mg of betamethasone = +/- 7 mg of prednisone equivalence
- 1 mg of cortisone = +/- 0.2 mg of prednisone equivalence
- 1 mg of dexamethasone = +/- 7 mg of prednisone equivalence
- 1 mg of hydrocortisone = +/- 0.25 mg of prednisone equivalence
- 1 mg of methylprednisolone = +/- 1 mg of prednisone equivalence
- 1 mg of prednisolone = +/- 1 mg of prednisone equivalence
- 1 mg of triamcinolone = +/- 1 mg of prednisone equivalence.

Finally, the cumulative oral/IV steroid dose (prednisone equivalent dose) per patient will be calculated as the sum of all prednisone equivalent doses taken by the patient each day during the duration of current COPD exacerbation.

7.1.4.17 BODE index

BMI

The BMI is to be calculated from the weight and height obtained at scheduled visits where the BODE index is required. BODE uses the binary classification for BMI > 21 kg/m² (scored as 0) or ≤ 21 kg/m² (scored as 1).

Obstruction

The level of obstruction for the BODE index will be collected from the spirometry done at the

timepoints where the BODE index is specified. The index to be used is the FEV1 (% predicted value). BODE uses the following classification for FEV1 (% predicted): $\geq 65\%$ (scored as 0), 50-64% (scored as 1), 36-49 % (scored as 2) or $\leq 35\%$ (scored as 3).

Dyspnoea (mMRC score)

The mMRC dyspnoea scale is a questionnaire that consists of five statements about perceived breathlessness: grade 0 (scored as 0), “I only get breathless with strenuous exercise”; grade 1 (scored as 0), “I get short of breath when hurrying on the level or up a slight hill”; grade 2 (scored as 1), “I walk slower than people of the same age on the level because of breathlessness or have to stop for breath when walking at my own pace on the level”; grade 3 (scored as 2), “I stop for breath after walking 100 yards or after a few minutes on the level”; grade 4 (scored as 3), “I am too breathless to leave the house”.

Exercise (6MWT)

The 6-Minute Walk Test (6MWT) to achieve the BODE index will be performed at scheduled visits when BODE index is required. It will be documented if it is not medically possible for the subject to perform the 6MWT. The subject will be required to walk as fast as he/she can without stopping for 6 minutes, in a pre-defined and scaled circuit supervised by a physician and with oxygen saturation monitoring.

The distance covered over 6 minutes will be recorded as well as the speed (if available) and the oxygen saturation. BODE uses the following classification for 6MWT (meters): ≥ 350 meters (scored as 0), 250-349 meters (scored as 1), 150-249 meters (scored as 2), ≤ 149 meters (scored as 3) or Not Done (scored as 3).

BODE Index

The BODE index is used to evaluate the functional status of subjects with COPD. Each parameter of the index (airflow obstruction, dyspnoea score per mMRC and exercise tolerance using the 6MWT) is graded from 0 to 3 with the exception of BMI which is graded as 0 or 1. The overall BODE score is the sum of all 4 individual scores and may vary from 0 to 10. (Refer Appendix E)

7.1.5 Definitions relative to safety parameters

7.1.5.1 Adverse Event (AE)

An AE is defined as any untoward medical occurrence in a subject, or clinical investigation subject administered a pharmaceutical product, and which does not necessarily have a causal relationship with this treatment. An AE can therefore be any unfavourable and unintended sign, symptom or disease temporally associated with the use of a medicinal (investigational) product, whether or not related to the medicinal (investigational) product.

7.1.5.2 Serious Adverse Event (SAE)

A Serious Adverse Event (SAE) is defined as an AE that results in one of the following outcomes:

- Results in death
- Is life-threatening
- Requires in-patient hospitalisation or prolongs existing hospitalisation (this does not include prolonged hospitalisation for study purposes)
- Results in persistent or significant disability/incapacity
- Is a congenital anomaly/birth defect
- Is an important medical event.

7.1.5.3 Duration of AEs

The duration of an AE will be calculated as the resolution date minus the date at which it first appeared plus 1.

In the case of an AE still continuing at the end of the study, the duration will be considered as unknown.

7.1.5.4 Relationship of AEs

The relationship between an AE and the study treatment (BCT197 or placebo) will be determined by the Investigator on the basis of his or her clinical judgment and the definitions in Table 7.

Table 7: Assessment of Relationship

Reasonable possibility of relatedness	
If there is enough evidence or argument to suggest the causal relationship. The investigator should consider, but not limited to, before reaching up to a decision on causality assessment:
 
 o Time relationship between study drug intake and event's onset o Dechallenge o Rechallenge o Medical History o Study treatment o Mechanism of action of study drug o Class effect o Concomitant treatments in use o Withdrawal of study treatment o Lack of efficacy/worsening of existing condition o Erroneous treatment with study medication or concomitant medication o Protocol related process.
No reasonable possibility of relatedness	o there are NOT enough evidence or argument to suggest the causal relationship

Adverse events will be considered causally related to the use of the IMP when the relationship is

not recorded. For pre-treatment adverse events, a causality assessment is not relevant.

7.1.5.5 Intensity of AEs

The Investigator will assess the intensity of AEs using the following definitions:

- Mild (awareness of sign or symptom, but easily tolerated)
- Moderate (discomfort sufficient to cause interference with normal activities)
- Severe (incapacitating, with inability to perform normal activities).

7.1.5.6 Adverse Event of Special Interest (AESI)

Following Adverse Events are of Special Interest:

- Pneumonia
- Liver injury (liver enzymes: ALT, AST, bilirubin total and fractions)
- Dermatologic events (Rash/Acneiform dermatitis/Pruritus)
- Headache
- Inflammation of cervix and vagina.

7.2 Handling of missing data and outliers

7.2.1 Missing data analysis methods

No strategy for imputation of missing values from subjects who dropped out will be applied because the mixed model for repeated measurements analysis done for the primary endpoint is known to produce a valid analysis if the drop-out mechanism is missing at random⁵.

The analysis (and clinical database) will only include those FEV1 results assessed as being of acceptable quality for each time point.

7.2.2 Handling of missing or incomplete dates

7.2.2.1 Partial dates of first COPD diagnosis

In order to calculate the COPD disease duration (i.e. time since first COPD diagnosis), the following rules will be applied for partial dates for first diagnosis of COPD:

- if the day of the month is missing it is imputed to be the 15th
- if both the day and month are missing, they are imputed to be June 30
- missing years will be left as missing.

The above will be flagged and described as a footnote in the appropriate listings.

7.2.2.2 Partial dates of current COPD exacerbation symptoms start/stop

In order to calculate the current COPD exacerbation duration (i.e. from the date when symptoms started until the date when symptoms stopped) and the times from start/stop of current COPD exacerbation to first dosing, the following rules will be applied for partial dates for current COPD exacerbation symptoms start and stop:

- if the day of the month is missing it is imputed to be the 15th
- missing months will be left as missing
- missing years will be left as missing.

The above will be flagged and described as a footnote in the appropriate listings.

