7.1.3.7 Times from start/stop of current COPD exacerbation to first dosing

Times from start/stop of current COPD exacerbation symptoms to first dose of study medication will be calculated in days as:
(date of first study treatment dose – date when symptoms started/stopped).

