7.1.4.10 Time to next COPD exacerbation

The time to next COPD exacerbation (in days) is defined as:

(Date when first COPD exacerbation symptoms started – Date when current COPD exacerbation symptoms stopped),

where COPD exacerbations experienced during the study are recorded on the ‘Acute Exacerbation COPD’ form of the eCRF, i.e.:

- Start date of COPD exacerbation is the ‘date when symptoms started’ recorded on the form
- COPD exacerbation has an intensity recorded as ‘Mild’, ‘Moderate’ or ‘Severe’ on the form.

Table 4: Criteria for event/censored for assessment of Time to next COPD exacerbation

Situation	Date of event or Censoring	Time to next COPD exacerbation	Outcome
Subjects who had next COPD exacerbation	Date of next COPD exacerbation after entering in study	Time from when current COPD exacerbation symptoms stopped until Date of next COPD exacerbation after entering in study	Event
Subjects who never had COPD exacerbation in study period	Withdrawal or last contact date	Time from when current COPD exacerbation symptoms stopped until Date of withdrawal or last contact date	Censored
Subjects who died	Death date	Time from when current COPD exacerbation symptoms stopped until Date of death	Censored
Subjects who withdrew or were lost to follow-up during the study	Withdrawal or last contact date	Time from when current COPD exacerbation symptoms stopped until Date of withdrawal or last contact date	Censored

7.1.4.11 Time from hospitalisation admission until subject is medically ready for discharge (current COPD)

This time (in days) will be calculated as:

(Date subject is medically ready for discharge from hospital – Date of hospitalisation admission),

where ‘Date of hospitalisation admission’ and ‘Date subject is medically ready for discharge from hospital’ are recorded on the ‘Current COPD Exacerbation’ form of the eCRF.

Table 5: Criteria for event/censored for assessment of Time from hospitalisation admission until subject is medically ready for discharge (current COPD)

Situation	Date of event or Censoring	Time from hospitalisation admission until subject is medically ready for discharge	Outcome
Subjects who were medically ready for discharge from hospital	Date subject is medically ready for discharge	Time from hospitalisation admission until Time subject is medically ready for discharge	Event

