8.6.2.1 Primary analysis

The primary analysis of efficacy will be based on the ITT population and observed cases.

The primary analysis will compare each of the treatment regimens together using pairwise comparison tests based on a mixed model for repeated measurements (MMRM) using an unstructured covariance matrix and the Kenward-Roger adjustment for the denominator degrees of freedom. The model will use FEV1 absolute changes at Days 2, 3, 4, 5, 6 and 7, and will include treatment [REDACTED] severity of airflow limitation at baseline (post-bronchodilator FEV1 at baseline (pre-dose) <30% or ≥30% of predicted normal value), blood eosinophils (%) value at baseline (<2% or ≥2%), time from start of current COPD exacerbation to first IMP dosing (≤2 days, 3-4 days or ≥5 days), presence of cardiovascular comorbidities at screening (yes, no) and COPD exacerbation treatment at screening (systemic corticosteroids only, antibiotics only or both systemic corticosteroids and antibiotics) as fixed effects and baseline FEV1 value as covariate. In addition the baseline FEV1 value-by-visit and the treatment-by-visit interactions will be included in the model.

LSMEAN and standard error (SE) of each treatment regimen as well as the adjusted mean difference between treatment regimens and associated two-sided 95% CIs will be obtained from the MMRM model at Days 2, 3, 4, 5, 6 and 7. Each pairwise treatment regimen comparison will be tested at an alpha level of 5%. Difference will be considered and confirmed between pairwise treatments if the two-sided P-value for the test for difference is below 0.05. P-values of the effects will also be presented.

Hypotheses:

The 'superiority' null hypothesis will be:

$H_0: T2-T1 = 0$ (T2 is equivalent to T1) vs the alternative

$H_a: T2-T1 \neq 0$ (T2 is different to T1)

MMRM model and SAS code:

The SAS code used to implement linear mixed model for repeated measures for FEV1 and 95% CIs of differences between treatments will be similar to that shown below:

PROC MIXED data = dataset;

CLASS ID trt visit severity eosino time_symp cv_comorb COPD_trt;

*MODEL change = trt visit trt*visit severity eosino time_symp cv_comorb COPD_trt baseline*

*baseline*visit / ddfm=KenwardRoger;*

REPEATED visit / subject=ID type=UN;

*LSMEANS trt*visit / cl;*

LSMEANS trt / cl;

*LSMESTIMATE trt*visit*

'A vs B: Visit 2' 1 0 0 0 0 0 -1 0 0 0 0 0 0 0 0 0 0 0,

'A vs B: Visit 3' 0 1 0 0 0 0 0 -1 0 0 0 0 0 0 0 0 0 0,

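### Setting a missing symptom start or stop day to the 15th, with no bound, can give impossible dates and lets the calendar decide the time-from-onset class

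*SAP*

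**What the plan says.** SAP 7.2.2.2 covers partial dates for the start and stop of the current exacerbation's symptoms. Its rule is that "if the day of the month is missing it is imputed to be the 15th", with the recorded month kept. If the month is absent, "missing months will be left as missing". Imputed dates are flagged and footnoted in the listings, but nothing ties them to first dose, to admission or to each other. The section states its purpose as the duration of the current exacerbation and "the times from start/stop of current COPD exacerbation to first dosing, the following rules will be applied for partial dates".

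These dates are used in several places:

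- **SAP 7.1.3.6:** symptom duration is stop minus start plus 1. Time to complete recovery is counted from the start date.
- **SAP 7.1.3.7:** the time to first dosing is "date of first study treatment dose – date when symptoms started/stopped".
- **SAP 8.6.1 and 8.6.2.1:** the primary model has as a fixed effect "time from start of current COPD exacerbation to first IMP dosing (≤2 days, 3-4 days or ≥5 days"). The same factor enters the other ANCOVA and repeated-measures models, and it is a subgroup in 8.8.3.
- **SAP 7.1.4.16:** steroid dose is summed "from the date when symptoms started until the date when symptoms stopped".
- **SAP 7.1.4.10:** time to next exacerbation is "Time from when current COPD exacerbation symptoms stopped until Date of next COPD exacerbation after entering in study".

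Protocol 9.3.1 (criterion 3) requires an active exacerbation at entry, and Protocol 9.1.1 places first dose after presentation with it.

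**The concern.** The true dates have known bounds: onset cannot follow first dose, and stop cannot precede onset or Day 1. A mid-month default ignores these. SAP 7.2.2.1 uses the same default for the date of COPD diagnosis, but there the result is in years and two weeks hardly matter. Here the covariate is cut at 2 and 4 days, so a shift of a few days changes the class. The neighbouring rules in 7.2.2.3 and 7.2.2.4 do refer partial dates to first dose or Visit 9.

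At stake are impossible values in derived durations, recovery times and steroid windows, and a covariate and subgroup that, for these patients, reflect the day of the month rather than how long they had been ill.

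**Working it through.** The plan gives no figure for this rule, so there is none to reproduce. The check is date arithmetic.

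**Onset lag.** Imputed lag = first-dose date − 15th of the onset month.

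| Onset month | Dose day of month | Imputed lag (days) | Class |
|---|---|---|---|
| Same as dosing | 1-14 | −14 to −1 | ≤2 |
| Same as dosing | 15-17 | 0 to 2 | ≤2 |
| Same as dosing | 18-19 | 3 to 4 | 3-4 |
| Same as dosing | 20 or later | 5 or more | ≥5 |
| Previous month | any | 14 or more | ≥5 |

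Within each case the class depends only on the day of the month.

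**How often.** For each of 365 dosing dates and each whole-day true lag, the onset day was replaced by 15 and the lag recomputed. Even dosing dates and uniform lags are assumptions; the documents give neither distribution.

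| True lag, uniform over | Onset after first dose | Correct class | Correct class if onset is capped at first dose |
|---|---|---|---|
| 0-7 days | 35% | 43% | 43% |
| 0-14 days | 23% | 57% | 57% |
| 0-21 days | 16% | 69% | 69% |

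At a true lag of 3 or 4 days, 93% land in the wrong class. Capping onset at first dose removes every negative lag but changes no class, because negative and zero lags both fall in ≤2 days.

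**Stop date.** The imputed stop differs from the true stop by −16 to +14 days, with a mean absolute error of 7.6 days. Illustrations:

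- Start known as the 20th, stop day missing in the same month: duration = 15 − 20 + 1 = −4 days, and the steroid window is empty.
- Start known as the 12th, first dose on the 18th, true stop on the 25th, stop day missing: the window closes on the 15th, so all steroid given after first dose is lost.
- Both days missing in one month: duration = 15 − 15 + 1 = 1 day, whatever the truth.

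On the same even dosing dates, the imputed stop precedes first dose in 41%, 28% and 18% of cases when the true stop is 3, 7 and 10 days after dosing.

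**Next exacerbation.** SAP 7.2.2.4 sets a day-missing onset of the next exacerbation to the 1st. If an imputed stop on the 15th of the same month is the origin, the time is 1 − 15 = −14 days. The SAP has no rule for negative times.

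**Primary contrast.** A simulation used 85 patients per arm, a true difference of 100 mL and SD 230 mL (SAP 5). It assumed lags uniform over 0-7 days and class effects of 0, −40 and −80 mL, and fitted a single-visit ANCOVA rather than the full MMRM. With 0%, 5%, 10%, 20% and 100% of onset days imputed, the mean estimate stayed at 99-100 mL, the SE rose from 35.4 to at most 35.8 mL, and power stayed at 79-81%.

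**The case against.** Only patients with a recorded month and a missing day are affected. These are recent dates, entered on a dedicated eCRF form for hospitalised patients seen daily to Day 7, so such cases may be isolated. Flagging in the listings would make odd values visible. Protocol 13.5.1 treats all analyses as exploratory. All of this stands, and it keeps the point minor. It does not make an onset after first dose acceptable as a programmed result.

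A reader might infer three stronger things that the documents do not support:

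- **That the rule is wrong more often than right.** This holds for lags of 0-7 days but reverses at 0-14 days. The documents give no onset-to-dose distribution, so no single error rate can be attached to the rule.
- **That the primary comparison is biased.** Onset precedes randomisation, and the misclassification does not depend on arm. The cost is a slight loss of precision.
- **That the imputed stop date certainly starts the clock for time to next exacerbation.** The scope sentence in 7.2.2.2 does not name that analysis. No other rule covers a partial stop date there, so this use is the natural reading, but it is unstated.

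**Conclusion.** The point holds as a minor correction. The written rule can produce onset after first dose, stop before start and stop before Day 1, which contradicts the trial's own entry conditions. The gain from correcting it lies mainly in valid durations, recovery times and steroid windows, and in a cleaner covariate and time-from-onset subgroup. The percentages apply only to imputed cases and rest on the assumed dosing dates and lags; the number of affected patients is unknown. The negligible effect on the primary contrast rests on the simulation's assumed class effects and on the covariate being fixed before randomisation.

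**What to change.** Before unblinding:

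1. In SAP 7.2.2.2, bound an imputed onset to no later than admission or first dose, whichever is earlier. Bound an imputed stop to no earlier than onset and Day 1, and no later than last contact.
2. In 8.6.1, 8.6.2.1 and 8.8.3, add an *unknown* level of the time-from-onset factor for a missing onset day or month. The plan has no such level now. It is needed because the bound does not correct the class, and it also keeps month-missing patients from being dropped under Appendix F, which excludes patients with a missing covariate.
3. Name every derivation that uses the imputed dates. In particular, say whether the imputed stop is the origin in 7.1.4.10, and how a zero or negative time is handled given the first-of-month rule in 7.2.2.4.

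The cost is a few sentences across these sections and one extra covariate level. No new data are needed.
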